3. INTRODUCTION

3.1. Purpose of this Document

This document provides a detailed description of the statistical methods and procedures to be implemented during the analysis of protocol SRS 1.0. The methods and procedures are intended to support the generation of a Clinical Study Report (CSR), including detailed descriptions of the populations and methodologies, as well as the post-text tables, analysis summary tables, patient data listings, and descriptive graphics.

This study is a prospective, multicenter, single-arm, open-label trial enrolling approximately 105 patients who are dependent on a urinary catheter. The primary objective is to determine the proportion of patients who achieve adequate bladder drainage over 90 days, defined as a post-void residual (PVR) of ≤ 150 ml. The pre-specified success criterion for this study is that ≥ 50 percent of patients will achieve adequate bladder drainage over 90 days.

The planned analyses identified in this statistical analysis plan (SAP) may be included in regulatory submissions and/or future manuscripts. Exploratory analyses, not identified in this SAP, may be performed to support the clinical development program. Any post-hoc, or unplanned, analyses that are performed but not identified in this SAP will be clearly identified in the CSR. The structure and content of this SAP provides sufficient detail to meet the requirements identified by the FDA and International Conference on Harmonization of Technical Requirements for Registration of Pharmaceuticals for Human Use (ICH): Guidance on Statistical Principles in Clinical Trials.

3.2. Supporting Documents

This SAP is intended to be used in conjunction with the following documents:

- The protocol, SRS 1.0
- The list of tables, listings, and figures, SRS SAP Index 2.0
- The templates of tables, listings, and figures, SRS TLF 1.0.

The template document shows all of the data that will be summarized, graphed or listed. For this reason, this document does not enumerate the data variables, but simply refers to the appropriate table, listing, or figure.

4. STUDY OBJECTIVES AND ENDPOINTS

4.1. Study Objectives

The primary objective of this study is to determine the proportion of patients who achieve adequate bladder drainage over 90 days, defined as a post-void residual (PVR) of ≤ 150 ml. The pre-specified success criterion for this study is that ≥ 50 percent of patients will achieve adequate bladder drainage at each of the 4 evaluations over 90 days. The primary objective will be met if

the one-sided lower bound of the 95% confidence limit for the incidence of patients who achieve adequate bladder drainage at each of the 4 evaluations over 90 days is $\geq 50\%$.

There are 5 secondary objectives, presented below in the order from the protocol.

- To measure the effects of the Spanner stent on bladder drainage, defined by the proportion of patients who achieve a post-void residual of ≤ 150 ml over 30 days.
- To measure the effects of the Spanner stent on bladder drainage, defined by the proportion of patients who achieve a post-void residual of ≤ 250 ml over 30 days.
- To measure the effects of the Spanner stent on bladder drainage, defined by the proportion of patients who achieve a post-void residual of ≤ 250 ml over 90 days.
- To measure the effects of the Spanner stent over time on maximum flow rate (Q_{max} in ml/sec) as assessed by Uroflow
- To measure the effects of the Spanner stent over time on the International Prostate Symptom Score (IPSS)

The 5 secondary objectives will be summarized and presented descriptively. No formal hypothesis test will be performed for the secondary objectives.

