14.1 Level of Significance, Power and Sample Size

A hypothesis test that the proportion of successes in the treatment group is statistically significantly greater than 50% will be computed. In order to have an 80% chance of showing that the success proportion in the Spanner group is statistically significantly greater than 50%, assuming that the device can achieve a 65% success rate, with $\alpha=0.05$, a sample size of $n=85$ completers will be needed for the study. The sample size calculation was based on an exact binomial one sample test.

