14.6.3 Analysis of the Primary Effectiveness Variable

The following hypotheses will be tested at a one-sided $\alpha=0.025$ level of significance:

$$H_{a0}: p_s \leq 50\% \quad \text{vs.} \quad H_{a1}: p_s > 50\%$$

where p_s is the proportion of subjects with maintenance of successful voiding during the Spanner implantation period. This hypothesis will be tested using a one-sample exact binomial test. Summary statistics (counts and percentages) will be computed on the primary endpoint along with a 95% confidence interval on the treatment group success proportion.

² A major protocol deviation is defined as any protocol deviation that may affect the primary endpoint.

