4.2.1. Primary Effectiveness Endpoint

PVR levels will be monitored throughout the 90 days of stent use to confirm that the patient is able to successfully empty his bladder. PVR levels are assessed on Visits 1, 2, 3 and 4 while stent is in place using abdominal ultrasound. The hypothesis is that over 90 days of stent use, 50% of the patients will be able to successfully empty their bladder, as defined by PVR of ≤ 150 ml at all four visits.

Patients where the PVR is >150 ml at 1 or more of the 4 visits will be considered a *treatment failure*. Patients who fail to attend any of the 4 scheduled visits, or withdraw prematurely, will also be treated in primary the analysis as a *treatment failure*. Patients where the PVR is <150 ml at all 4 visits will be considered a *treatment success*.

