5.3. Sample Size Justification

In order to have an 80% chance of showing that the success proportion in the Spanner group is statistically significantly greater than 50%, assuming that the device can achieve a 65% success rate, with a two-sided type 1 error rate of 5%, a sample size of $n=85$ completers will be needed for the study. Assuming that a one-sided type 1 error rate of 5% will be adequate, the sample size of 85 completers will provide 88% power. Completers are those subjects whose endpoint is known at 90 days.

Assuming a dropout rate of 20%, the total sample size of $n=105$ patients will be required for the study. Dropouts are those patients who exit the study prior to completing 90 days without experiencing a PVR failure. The sample size calculation was based on an exact binomial one sample test using PASS 14.0.9 (PASS 14 Power Analysis and Sample Size Software (2015). NCSS, LLC. Kaysville, Utah, USA, ncss.com/software/pass.)

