13.2. Primary Effectiveness Endpoint Analysis

The results of the Primary Effectiveness Endpoint analysis will be presented in the SRS TLF, Table 31.

The primary effectiveness endpoint for this study is the proportion of patients who achieve adequate bladder drainage over 90 days, defined as a post-void residual (PVR) of ≤ 150 ml. The pre-specified success criterion for this study is that ≥ 50 percent of patients will achieve adequate bladder drainage at each of the 4 evaluations over 90 days. The primary objective will be met if the one-sided lower bound of the 95% confidence limit for the incidence of patients who achieve adequate bladder drainage at each of the 4 evaluations over 90 days is $\geq 50\%$. The null and alternative hypotheses are as follows:

$$H_0: \pi \leq 0.5$$

$$H_a: \pi > 0.5$$

π is the proportion of patients with maintenance of successful voiding during the Spanner implantation period.

Results based on the ITT population will be presented in Table 32 entitled *Primary Effectiveness Endpoint Analysis* (PVR of ≤ 150 ml) (ITT population). The table will contain the point estimate and the confidence limit based on patients who met the primary endpoint.

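### The primary test has two significance levels: one-sided 2.5% in Protocol 14.6.3 and, on the natural reading, one-sided 5% in the SAP success rule

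*SAP*

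**What the plan says.** - **Protocol 14.6.3:** "The following hypotheses will be tested at a one-sided $\alpha=0.025$ level of significance", with a null of at most 50%. It continues: "This hypothesis will be tested using a one-sample exact binomial test". A 95% confidence interval is reported alongside.
- **SAP 4.1 and 13.2:** the null and alternative in SAP 13.2 are the same, but the decision rule is put as a bound. SAP 4.1 requires "the one-sided lower bound of the 95% confidence limit for the incidence of patients who achieve adequate bladder drainage" to be 50% or more, and SAP 13.2 repeats the rule: "The primary objective will be met if the one-sided lower bound of the 95% confidence limit" is at 50% or more. Neither section names a method for the interval.
- **SAP 5.3:** two error rates appear in succession. The first is "with a two-sided type 1 error rate of 5%, a sample size of $n=85$ completers will be needed for the study", for 80% power at a true rate of 65%. The second is "Assuming that a one-sided type 1 error rate of 5% will be adequate, the sample size of 85 completers will provide 88% power". No reason is given for the second, and the section does not say that it replaces the protocol's 0.025.
- **SAP 8:** p-values below 0.05 count as statistically significant, with no exception for a one-sided primary test.
- **Protocol 14.1:** alpha is 0.05, without saying whether one- or two-sided.
- **Protocol 8.1 and SAP 3.1, 4.1 and 13.2:** the pre-specified success criterion is also stated simply as at least 50 percent of subjects succeeding.

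**The concern.** This is the trial's only confirmatory test, since SAP 4.1 makes every secondary objective descriptive. Its pass mark ought to be a single number fixed in advance. Here the protocol sets one level, and the document that will be used for the analysis sets a nominal level twice as large. Protocol 14.7 hands only the secondary analyses to the SAP, SAP 3.2 says the SAP is to be used together with the protocol, and no clause in the text available ranks the two. In an open-label, single-arm study, a result in the narrow band between the two marks could be reported as a success or a failure depending on which document is followed.

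**Working it through.** **Inputs.** Null 50%, assumed true rate 65%, 85 completers, 105 enrolled, 20% dropout (Protocol 14.1 and 14.2; SAP 5.3). One-sided 0.025 comes from Protocol 14.6.3 and one-sided 0.05 from the SAP rule.

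**1. Reproduce the plan's figures.** By normal approximation, power = Φ((0.15·√n − z·0.5)/√(0.65·0.35)). At n = 85:
- z = 1.96 gives 80.1%, and the required n is ((1.96·0.5 + 0.842·0.477)/0.15)² = 84.8, rounded up to 85.
- z = 1.645 gives 88.0%.

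So the 80% belongs to one-sided 2.5% and the 88% to one-sided 5%. SAP 5.3 treats them as different levels.

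**2. Exact pass marks.** The mark is the smallest x with P(X ≥ x | n, 0.5) at or below alpha. This is the same as the Clopper-Pearson lower limit at that alpha being at least 50%.

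| n | x | P(X ≥ x) at 50% | One-sided 95% lower limit | Two-sided 95% lower limit |
|---|---|---|---|---|
| 105 | 61 | 0.0590 | 49.6% | 48.1% |
| 105 | 62 | 0.0392 | 50.6% | 49.0% |
| 105 | 63 | 0.0252 | 51.5% | 49.98% |
| 105 | 64 | 0.0157 | 52.5% | 50.9% |
| 85 | 50 | 0.0642 | 49.3% | 47.6% |
| 85 | 51 | 0.0410 | 50.5% | 48.8% |
| 85 | 52 | 0.0251 | 51.7% | 49.99% |
| 85 | 53 | 0.0147 | 52.9% | 51.2% |

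The marks are 64 (protocol) against 62 (SAP) of 105, and 53 against 51 of 85. At n = 84, which is 80% of 105, they are 52 against 51. The gap is therefore one or two subjects.

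**3. How often the rules disagree.**
- *All 105 subjects, withdrawals counted as failures* (Protocol 14.3, SAP 4.2.1). With 20% dropout, the all-subject rate is 0.8 × 0.65 = 0.52. P(X ≥ 62) = 8.9% and P(X ≥ 64) = 4.1%, so the rules disagree in 4.8% of trials.
- *85 completers at 65%.* P(X ≥ 51) = 86.0% and P(X ≥ 53) = 73.6%, so they disagree in 12.3%.
- *84 completers at 65%.* 82.6% and 76.3%, so they disagree in 6.4%.

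**4. The literal 50 percent criterion.** Read as an observed rate, it is met at 53 of 105 (50.5%). Because 105 is odd, P(X ≥ 53) at a true rate of 50% is exactly one half. It cannot be the decision rule, but it stands in the same SAP paragraphs.

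**The case against.** **The SAP may mean the lower end of a two-sided 95% interval.** That would be one-sided 2.5% and would agree with the protocol. The wording is loose enough to allow it, and Protocol 14.6.3 itself reports a 95% interval. This stands as a caveat. Against it are the word one-sided in the rule and the separate one-sided 5% sentence in SAP 5.3, whose 88% is reproduced only at that level. Even if the two-sided reading was intended, the rule needs rewording.

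**A reader might infer that the threshold will be picked after the result is seen.** The documents do not support that. Protocol 14.7 requires the SAP to be signed before the first enrolment, and Protocol 14.10 requires deviations from the planned analysis to be described and justified. These provisions do not settle which document governs, so a late choice is possible but not certain.

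**A reader might infer that the SAP rule exceeds 5% error.** With an exact bound it does not (3.9% at 105, 4.1% at 85). A one-sided Wilson or Wald bound would lower the mark at 105 to 61, with 5.9% error, but the SAP names no method.

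**The band is narrow.** This is true. On the analysis closest to the stated primary one, with the plan's own dropout, both rules pass fewer than 9% of trials. That limits how often the conflict would matter but does not remove it.

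**Conclusion.** The conflict is real and must be resolved before analysis. The protocol tests at one-sided 0.025; the SAP's rule, on its natural reading, uses one-sided 0.05. A result of 62 or 63 of 105 (59.0% to 60.0%), or 51 or 52 of 85 (60.0% to 61.2%), passes one and fails the other.

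These marks assume an exact bound and a fixed binary denominator. Under the multiple imputation of Protocol 14.11 a single integer mark need not apply, and SAP 8's observed-data presentation would use a different denominator. Those choices change the size of the band but not the contradiction in alpha.

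It would be too narrow to say that the divergence lies only in the SAP success rule and the one sentence of SAP 5.3. The 0.05 convention in SAP 8 points the same way, and a repair that leaves it in place is incomplete.

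**What to change.** - **SAP 4.1 and 13.2:** state that success requires a one-sided exact binomial p-value of at most 0.025, that is, a lower limit of the two-sided 95% Clopper-Pearson interval of at least 50%.
- **SAP 3.1, 4.1 and 13.2 and Protocol 8.1:** state that this test, and not an observed rate of at least 50%, is the success criterion.
- **SAP 8:** exempt the one-sided primary test (0.025) from the 0.05 convention.
- **SAP 5.3:** delete the sentence adopting one-sided 5% with 88% power.
- **Protocol 14.1:** say that alpha = 0.05 is two-sided, as SAP 5.3 already does for the same calculation.
- **If the sponsor prefers one-sided 5%:** amend Protocol 14.6.3 explicitly, with a justification, before data are seen, and align the SAP with it.

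The cost is text edits, with no change to enrolment or conduct. The downside for the sponsor is a pass mark one or two subjects higher than the SAP's.

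A separate correction belongs in the same sections. Protocol 14.1 says "The sample size calculation was based on an exact binomial one sample test", and SAP 5.3 says the same, yet the stated 80% matches the normal approximation. The exact test gives 73.6% at one-sided 0.025 with 85 completers at 65%. A mark of 52 would give 80.4%, but its error of 0.0251 is just over the limit. The power figure should be restated; reconciling alpha does not depend on it.

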4.2. Endpoints

The data from this clinical investigation will be based on the investigator / site reported information.

4.2.1. Primary Effectiveness Endpoint

PVR levels will be monitored throughout the 90 days of stent use to confirm that the patient is able to successfully empty his bladder. PVR levels are assessed on Visits 1, 2, 3 and 4 while stent is in place using abdominal ultrasound. The hypothesis is that over 90 days of stent use, 50% of the patients will be able to successfully empty their bladder, as defined by PVR of ≤ 150 ml at all four visits.

Patients where the PVR is >150 ml at 1 or more of the 4 visits will be considered a *treatment failure*. Patients who fail to attend any of the 4 scheduled visits, or withdraw prematurely, will also be treated in primary the analysis as a *treatment failure*. Patients where the PVR is <150 ml at all 4 visits will be considered a *treatment success*.

4.2.2. Secondary Effectiveness Endpoints

There are 3 secondary effectiveness endpoints:

Secondary Effectiveness Endpoint No. 1

- Patients with a PVR through the first removal visit is ≤ 150 ml of urine (visit 1 and 2) will be considered as having achieved the first secondary effectiveness endpoint. Patients where the PVR is >150 ml at visit 1 or 2 will be considered as having failed to achieve the first secondary effectiveness endpoint. Patients who fail to attend both scheduled visits, or withdraw prematurely from the study prior to visit 2 will be considered as having failed to achieve the first secondary effectiveness endpoint.

Secondary Effectiveness Endpoint No. 2

● Patients with a PVR through the first removal visit is ≤ 250 ml of urine (visit 1 and 2) will be considered as having achieved the second secondary effectiveness endpoint. Patients where the PVR is >250 ml at visit 1 or 2 will be considered as having failed to achieve the second secondary effectiveness endpoint. Patients who fail to attend both scheduled visits, or withdraw prematurely from the study prior to visit 2 will be considered as having failed to achieve the second secondary effectiveness endpoint.

Secondary Effectiveness Endpoint No. 3

● Patients with a PVR through the third removal visit is ≤ 250 ml of urine (visits 1, 2, 3 and 4) will be considered as having achieved the third secondary effectiveness endpoint. Patients where the PVR is >250 ml at any of the 4 visits will be considered as having failed to achieve the third secondary effectiveness endpoint. Patients who fail to attend all 4 scheduled visits, or withdraw prematurely from the study, will be considered as having failed to achieve the third secondary effectiveness endpoint.

4.2.3. Exploratory Effectiveness Endpoints

There are 2 additional exploratory endpoints that will be evaluated in this study:

Exploratory Effectiveness Endpoint No. 1

● Change from baseline (visit 1) at visits 2, 3, and 4 in the maximum flow rate (Q_{max} in ml/sec) as assessed by Uroflow

Exploratory Effectiveness Endpoint No. 2

● Change from baseline (visit 2) at visits 3 and 4 in the IPSS Total Symptom Score

Each of the 7 questions that compose the IPSS will be scored on a 0 to 5 scale. The total score can range from 0 to 35. An IPSS Total Symptom Score of 1-7 is considered *Mild*, 8-19 is considered *Moderate*, and 20-35 is considered *Severe*.

5. STUDY OVERVIEW

5.1. Study Design

This clinical investigation is a prospective, multicenter, single-arm, open-label trial enrolling approximately 105 patients who are dependent on a urinary catheter. Patients will be fitted with a Spanner stent and the stent will be replaced at an interval of approximately 30 days for a total of up to 90 days of use. The Spanner Temporary Prostatic Stent is intended for temporary use (up to 30 days) to maintain urine flow and allow voluntary urination for patients who are not candidates for pharmacologic, minimally invasive or surgical treatment of the prostate. Patients will complete the study upon removal of the Spanner stent after 90 days and one follow-up telephone call post-removal. PVR, uroflow, urinary symptoms, patient satisfaction and the occurrence of adverse events will be collected. Cystoscopy will be performed prior to the initial stent placement and

after the final stent removal to determine any effects of The Spanner on lower urinary tract anatomy.

5.2. Study Procedure

Screening is planned to be conducted entirely at Visit 1. Patients who meet the inclusion and exclusion criteria will be enrolled in the study. Device insertion is planned to be conducted at Visit 1. The study will be conducted at three to ten study centers in the US. The study will enroll approximately 105 patients who are dependent on a urinary catheter and meet eligibility criteria. The study will consist of a 90 day treatment period. Patients will be fitted with a Spanner stent and the stent will be replaced at an interval of approximately 30 days (25-35 days permitted) for a total of up to 90 days of use (75-105 days permitted). Patients will complete the study upon removal of the Spanner stent after 90 days and one follow-up telephone call post-removal.

All participants will undergo approximately 90 days of Spanner use, in the form of consecutive Spanner placements each lasting approximately 30 days (25-35 days permitted). During the 90 days, data will be collected with respect to PVR, uroflow, urinary symptoms, patient satisfaction and the occurrence of adverse events. Cystoscopy will be performed prior to the initial stent placement and after the final stent removal to determine any effects of The Spanner on lower urinary tract anatomy.

5.3. Sample Size Justification

In order to have an 80% chance of showing that the success proportion in the Spanner group is statistically significantly greater than 50%, assuming that the device can achieve a 65% success rate, with a two-sided type 1 error rate of 5%, a sample size of $n=85$ completers will be needed for the study. Assuming that a one-sided type 1 error rate of 5% will be adequate, the sample size of 85 completers will provide 88% power. Completers are those subjects whose endpoint is known at 90 days.

Assuming a dropout rate of 20%, the total sample size of $n=105$ patients will be required for the study. Dropouts are those patients who exit the study prior to completing 90 days without experiencing a PVR failure. The sample size calculation was based on an exact binomial one sample test using PASS 14.0.9 (PASS 14 Power Analysis and Sample Size Software (2015). NCSS, LLC. Kaysville, Utah, USA, ncss.com/software/pass.)

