14.2 Expected Drop-out Rates

Assuming a dropout rate of 20%, the total sample size of $n=105$ subjects will be required for the study. A hypothesis test that the proportion of successes in the treatment group is statistically significantly greater than 50% will be computed.

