14.3 Primary Effectiveness Variable and Pass/Fail Criteria

The primary effectiveness endpoint is the success/failure of the subject to have a successful urinary void at all four study visits: (a) upon initial placement of the first stent (Visit 1), and (b) at all three visits in which the subject has a stent placed for 30 days (Visits 2, 3 and 4).

The primary effectiveness endpoint will be marked as a failure for a subject if any of the following occur:

- PVR of >150 ml at any visit (Visits 1, 2, 3, and 4)
- The subject withdraws from the trial

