14.6.1 Analysis Populations

The following analysis populations will be defined.

- Intent-to-Treat (ITT) Population – The ITT population will consist of any enrolled subject who underwent an attempted Spanner device implant procedure.
- Per Protocol (PP) Population – The PP population will consist of all subjects who are enrolled in the study, have been implanted with a Spanner device, and have completed all study visits with no major protocol deviations while enrolled in the study².
- Safety Population – The safety population will consist of all subjects who are enrolled in the study.

The analysis of the primary and secondary efficacy endpoints will be conducted on ITT and PP populations. The primary analysis set will be the ITT analysis. All safety analyses will be conducted on the safety population.

The study subjects to be excluded from the PP analysis set and the reasons for their exclusion will be determined and documented prior to statistical analysis. These decisions will not be outcome-data driven.

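### The exact binomial test named in SAP 5.3 has 73.6% power with 85 completers at two-sided 5%, not 80%, and the completer basis conflicts with counting withdrawals as failures

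*SAP*

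**What the plan says.** SAP 5.3 assumes a true success rate of 65% against a null of 50%. It gives 85 completers for 80% power at two-sided 5%, and adds that at one-sided 5% "the sample size of 85 completers will provide 88% power". The method is stated as "The sample size calculation was based on an exact binomial one sample test using PASS 14.0.9". Protocol 14.1 gives the same number, target power and method ("The sample size calculation was based on an exact binomial one sample test"), with alpha 0.05 and no statement of sidedness.

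On who is counted, SAP 5.3 says "Completers are those subjects whose endpoint is known at 90 days" and "Dropouts are those patients who exit the study prior to completing 90 days without experiencing a PVR failure". With 20% dropout, SAP 5.3 and Protocol 14.2 arrive at 105 patients.

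On the analysis:

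- **Test and level.** Protocol 14.6.3 plans a one-sample exact binomial test at one-sided 0.025. SAP 4.1 and 13.2 declare success if a one-sided 95% lower confidence bound is at least 50%, and do not name the interval method.
- **Withdrawals.** Protocol 14.3 lists "The subject withdraws from the trial" as a reason to score the primary endpoint as a failure. SAP 4.2.1 does the same for withdrawals and missed visits. Protocol 14.6.1 says "The primary analysis set will be the ITT analysis".
- **Other missing-data rules.** SAP 8 makes observed data the primary presentation and failure imputation a worst-case sensitivity analysis. Protocol 14.11 prescribes multiple imputation.

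**The concern.** There are two separate problems.

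First, both documents attribute the power to an exact test, and Protocol 14.6.3 plans to use that test. An exact test on 85 patients can reject only at whole-number cutoffs, so its true type 1 error is usually below the nominal level and its power below the normal-approximation value. The stated 80% and 88% needed checking against the test that is named.

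Second, adding 20% for dropouts makes sense only if dropouts leave the denominator. Under Protocol 14.3 and SAP 4.2.1 they stay in it as failures, which lowers the success rate being tested. A power figure for 85 observed completers then says little about the chance that the primary analysis succeeds.

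**Working it through.** **Inputs.** n = 85 completers, p0 = 0.50, p1 = 0.65, two-sided 5% (upper tail 0.025) or one-sided 5%, 20% dropout, 105 enrolled. All are from SAP 5.3.

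**Reproducing the stated figures.** The normal approximation uses the null standard error for the cutoff and the alternative standard error for power:

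power = Φ[(0.15·√85 − z·√(0.5·0.5)) / √(0.65·0.35)]

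- z = 1.960: Φ(0.845) = 80.1%
- z = 1.645: Φ(1.175) = 88.0%

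The same formula gives n = 85 for 80% power at 0.025. Both stated figures match, though the documents do not say that this formula was used.

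**The named test.** Take the smallest k with P(X ≥ k | 85, 0.5) ≤ alpha; power is P(X ≥ k | 85, 0.65).

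| k | Upper tail at 50% | Power at 65% |
|---|---|---|
| 50 | 0.0642 | 90.3% |
| 51 | 0.0410 | 86.0% |
| 52 | 0.02513 | 80.4% |
| 53 | 0.0147 | 73.6% |

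- Upper tail 0.025: 52 just fails (two-sided p = 0.0503), so k = 53 and power is 73.6%, which is 6.4 points below 80%.
- One-sided 0.05: k = 51 and power is 86.0%, which is 2.0 points below 88%.
- The planned dropout leaves 105 × 0.8 = 84 completers. Exact power is then 76.3% (k = 52) or 82.6% (k = 51).
- The smallest n with 80% exact power at 0.025 is 90 (k = 55, 81.2%).

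**The confidence bound.** The cutoff under the SAP rule depends on the interval method, which is not named.

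- At 0.025, the Clopper-Pearson lower bound is 0.49988 for 52/85 and 0.5118 for 53/85, so 53 are needed (73.6%). The bound for 52/85 is 0.5055 by Wilson and 0.5082 by Wald, so both accept 52 (80.4%, true error 2.51%).
- At 0.05, Clopper-Pearson (0.5051 for 51/85) and Wilson (0.4990 for 50/85, 0.5108 for 51/85) need 51 (86.0%, true error 4.1%). Wald (0.5004 for 50/85) accepts 50 (90.3%, true error 6.4%).

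**Withdrawals scored as failures.** Assume all 105 are analysed, a fraction d drops out and fails, and 65% of the rest succeed. The tested rate is 0.65 × (1 − d). The exact cutoffs are 64 of 105 (0.025) and 62 of 105 (0.05).

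| Dropout d | Tested rate | Power at 0.025 | Power at 0.05 |
|---|---|---|---|
| 20% | 52.0% | 4.1% | 8.9% |
| 10% | 58.5% | 34% | 50% |
| 5% | 61.75% | 61% | 75% |
| 0%, or 65% already the ITT rate | 65.0% | 83.5% | 91.5% |

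Under this scoring, 80% power requires dropout of at most 0.9% (0.025) or 3.8% (0.05). At 20% dropout it requires a completer success rate of about 80.5% or 78.2%.

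Power under multiple imputation cannot be computed, because no imputation model is given.

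**The case against.** The arithmetic is not in dispute; the case against concerns weight.

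- **The 6.4-point gap is partly a quirk of n = 85.** The count of 52 misses 0.025 by 0.000125, and exact power moves in a sawtooth: 78.8% at n = 83, 76.3% at 84, 73.6% at 85, 78.0% at 86 and 79.7% at 88. This is fair. The completer count is unlikely to be exactly 85, and the shortfall at neighbouring values is smaller. It is still a shortfall at each of them, and 85 is the number for which the plan states 80%.
- **Under the SAP's own success rule the gap is minor.** With an exact or Wilson one-sided 95% bound, power is 86.0% against 88%. This stands. The larger gap applies to the two-sided 5% of SAP 5.3 and the one-sided 0.025 of Protocol 14.6.3.
- **The completer basis fits the observed-data rule in SAP 8.** That is true, so the mismatch is with Protocol 14.3 and SAP 4.2.1, and the cause is that the missing-data rules have not been reconciled.
- **The 4.1% and 8.9% figures stack assumptions.** They need failure scoring to govern, 65% to be the completer rate, and dropout to reach 20%. They should not be quoted without the favourable reading of 83.5% and 91.5%. That reading is less well supported, because no dropout inflation would be needed if 65% already counted withdrawals as failures.

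**Conclusion.** The concern holds on both parts.

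The stated power is not that of the named test: 73.6% instead of 80% at two-sided 5% or one-sided 0.025, and 86.0% instead of 88% at one-sided 0.05, for 85 completers. The first gap is material and the second small. This part rests only on the inputs in SAP 5.3.

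The completer basis also does not describe a primary analysis that scores withdrawals as failures. Across the cases worked above, power in that analysis runs from 4.1% (20% dropout, 65% as the completer rate, one-sided 0.025) to 91.5% (65% as the ITT rate, one-sided 0.05). The plan does not say which case applies. The natural reading of SAP 5.3 is that 65% is the completer rate, but that remains an assumption. This should be fixed.

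**What to change.** 1. In SAP 5.3 and Protocol 14.1, restate the exact-test power for 85 completers as 73.6% (two-sided 5%, one-sided 0.025) and 86.0% (one-sided 0.05), or label 80% and 88% as normal-approximation values. State that these figures apply to 85 observed completers only.
2. Settle one primary missing-data rule (Protocol 14.3 and SAP 4.2.1 against SAP 8 and Protocol 14.11) and one alpha (Protocol 14.6.3 against SAP 4.1 and 13.2).
3. Name an exact (Clopper-Pearson) interval in SAP 4.1 and 13.2, so that the bound agrees with the exact test.
4. Say whether 65% is the completer or the ITT rate, then state the power of the primary analysis under the chosen rule.

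This is rewording; the correction itself changes no enrolment, test or endpoint. The cost is a less favourable stated power for the named test, and possibly a much lower one if withdrawals count as failures. The figure would not fall below 80% with a Wilson or Wald bound at 0.025 (80.4%), would not fall below 88% with a Wald bound at 0.05 (90.3%, at a true error of 6.4%), and would not fall below either target if 65% is the ITT rate. The direction under multiple imputation is unknown.
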